6.3.7. Last Contact Date

The last contact date will be derived using the last complete date in the eCRF on or before the data cutoff date, from among the following:

- All assessment dates (eg, vital signs assessment, ECG assessment)
- Dates of administration of study drug, concomitant medications, and subsequent anticancer therapies
- Start and end dates of AEs
- Last contact date collected on the Survival Follow-up eCRF when the subject status is alive
- Randomization date
- Withdrawal of consent date
- Date of discontinuation on disposition eCRF pages. If the option “Lost to Follow-up” is selected, the corresponding date will not be used in the derivation of last contact date

Notes:

- Only dates associated with actual examinations of the subject will be used in the derivation. Dates associated with a technical operation unrelated to subject status, such as the date a blood sample is processed, will not be used.
- Assessment dates after the data cutoff date will not be used to derive the last contact date.

6.4. General Methods

6.4.1. Data Handling After Cutoff Date

Data after the cutoff date may not undergo the cleaning process and will not be displayed in any listings or used for summary statistics, statistical analyses, or imputations.

6.4.2. Standard Derivations and Reporting Conventions

The following conversion factors will be used to convert days into weeks, months or years: 1 week=7 days, 1 month=30.4375 days, and 1 year=365.25 days.

The following derivations will be implemented.

- Age (years):
 - $(\text{date of informed consent} - \text{date of birth} + 1) / 365.25$
 - If only day of birth is missing: Age (years): $(\text{year/month of informed consent} - \text{year/month of birth})$
 - If day and month of birth are missing: Age (years): $(\text{year of informed consent} - \text{year of birth})$

The integer part of the calculated age will be used for reporting purposes.

- $\text{BMI (kg/m}^2\text{)} = \text{weight (kg)/height (m)}^2$
- BSA (m^2) as collected in the eCRF
- Duration (in days) from a reference date (eg, randomization date, start date of study treatment)=
 - date of event–reference date+1, if the date of the event is on or after the reference date
 - date of event–reference date, if the date of the event is before the reference date

Reporting conventions will be as follows:

- Mean and median will be displayed to one more decimal place than the raw data
- Standard deviation (SD) will be displayed to two more decimal places than the raw data
- Percentages will be displayed to 1 decimal place (however, percentages corresponding to 0 counts will be reported as 0 rather than 0.0 and 100 percent will be reported as 100 rather than 100.0)
- p-values will be reported with 4 decimal places; all p-values should be specified to be 1-sided or 2-sided
- Unless otherwise specified, rounding will be performed to the closest integer/first decimal using the common mid-point between the two consecutive values, eg, 5.11 to 5.14 will be rounded to 5.1, and 5.15 to 5.19 will be rounded to 5.2
 - Non-zero percentages that are <0.1 before rounding will be displayed as “<0.1”, eg, 0.09 will be reported as <0.1 rather than as 0.1
 - p-values <0.0001 before rounding will be displayed as “<0.0001”, eg, a p-value of 0.00009 will be displayed as <0.0001 rather than as 0.0001

6.4.3. Pooling of Data Across Sites

In order to provide overall estimates of treatment effects, data will be pooled across sites. The “site” factor will not be considered in statistical models or subgroup analyses given the high number of participating sites in contrast to the anticipated small number of subjects randomized at each site.

6.4.4. Continuous and Categorical Variables

Continuous variables will be summarized using descriptive statistics, ie, number of non-missing values, mean, standard deviation (SD), median, quartiles, minimum, and maximum. Time-to-event endpoints in the presence of censoring will be estimated using Kaplan-Meier (KM) methodology.

Categorical variables will be summarized by frequency distributions (number and percentage of subjects within a given category in the analysis data set). Unless otherwise specified, the calculation of percentages will include the “missing” category. Therefore,

counts of missing observations will be included in the denominator and presented as a separate category. For summaries by visit, percentages will be based on the number of subjects with data available for that visit, unless otherwise specified.

6.4.5. Unscheduled Visits

Generally, data collected at unscheduled visits will be included and summarized for both safety and efficacy analyses in the same manner as the data collected at scheduled visits. Descriptive statistics (mean, SD, median, quartiles, minimum, and maximum) by nominal visit for safety endpoints such as laboratory measurements, ECG parameters and vital signs will include only data from scheduled visits. Summaries of outliers [eg, worst value, worst change from baseline, worst Common Terminology Criteria for Adverse Events (CTCAE) grade] during the on-treatment period for safety endpoints such as AEs, laboratory measurements and ECG parameters will include data from both scheduled and unscheduled visits.

6.5. Methods for Handling Missing Data

6.5.1. Adverse Event and Concomitant Medication Start Dates

If the end date is non-missing and the imputed start date is after the end date, the end date will be used as the start date.

(1) Missing day only

- If the month and year are the same as the month and year of the date of the start of study treatment, the date of the start of study treatment will be used.
- If the month and year are before the month and year of the date of the start of study treatment, the last day of the month will be used.
- If the month and year are after the month and year of the date of the start of study treatment, the first day of the month will be used.

(2) Missing day and month

- If the year is the same as the year of the date of the start of study treatment, the date of the start of study treatment will be used.
- If the year is before the year of the date of the start of study treatment, 31 December will be used.
- If the year is after the year of the date of the start of study treatment, 01 January will be used.

(3) Missing day, month, and year

- The date of the start of study treatment will be used.

6.5.2. Adverse Event and Concomitant Medication End Dates

If the start date is non-missing and the imputed end date is before the start date, the start date will be used as the end date. If the death date is available and the imputed end date is after

the death date, the death date will be used as the end date. If an imputation for an AE end date results in an AE end date that is after the data cutoff date, the AE will be considered as ongoing at the data cutoff date.

(1) *Missing day only*

- The last day of the month will be used.

(2) *Missing day and month*

- 31 December will be used.

(3) *Missing day, month, and year*

- The event will be regarded as ongoing.

6.5.3. Exposure

No imputation will be done for the date of the first dose of study drug.

If the date of the last dose of study drug (AG-120 or matched placebo) is missing or partially missing, it will be imputed as follows:

- If the last date of study drug is completely missing and there is no End of Treatment Disposition eCRF page for the study drug AND there is no death date, the subject should be considered to be ongoing and the data cutoff date for the analysis will be used as the last dosing date.
- If the last date of study drug is completely or partially missing and there is EITHER an End of Treatment Disposition eCRF page for the study drug OR a death date (on or before the data cutoff date), then the imputed last dose date is:
=Last day of the year, if only the year is available and Year <Year of min (EOT date, death date)
=Last day of the month, if both the year and month are available and Year=Year of min(EOT date, death date) and Month <Month of min(EOT date, death date)
=min(EOT date, death date), for all other cases

If the date of the last dose of study drug (azacitidine) is missing or partially missing, it will be imputed as follows:

- If the last date of study drug is completely missing and there is no End of Treatment Disposition eCRF page for the study drug AND there is no death date, the subject should be considered to be ongoing and the latest complete dosing date on or before the data cutoff date will be used as the last dosing date.
- If the last date of study drug is completely or partially missing and there is EITHER an End of Treatment Disposition eCRF page for the study drug OR a death date (on or before the data cutoff date), then the imputed last dose date is:
=max(the latest complete dosing date on or before the data cutoff date, 01 January of the year), if only the year is available

=max(the latest complete dosing date on or before the data cutoff date, first day of the month), if both the year and month are available

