6.3.5. On-Treatment Period

The on-treatment period starts on the date of the start of study treatment and ends 28 days after the end of study treatment.

Data listings will include all assessments and events, with those that occur outside of the on-treatment period flagged.

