YYYY=Year of min[max(relapse date+1, last dose of study treatment+1), end date of new anticancer therapy], AND

MMM=Month of min[max(relapse date+1 day, last dose of study treatment+1 day), end date of new anticancer therapy]

THEN

imputed start date=min[max(relapse date+1 day, last dose of study treatment+1 day), end date of new anticancer therapy];

ELSE IF

YYYY=Year of min[max(relapse date+1, last dose of study treatment+1), end date of new anticancer therapy], AND

MMM >Month of min[max(relapse date+1 day, last dose of study treatment+1 day), end date of new anticancer therapy]

THEN

imputed start date=01 MMM YYYY;

ELSE IF

```
        YYYY <Year of min[max(relapse date+1, last dose of study  
        treatment+1), end date of new anticancer therapy]  
    THEN  
        imputed start date=DAY (Last day of MMM) MMM YYYY  
    ELSE IF  
        YYYY >Year of min[max(relapse date+1, last dose of study  
        treatment+1), end date of new anticancer therapy]  
    THEN  
        imputed start date=01 MMM YYYY.
```

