7.4.1. Treatment Duration and Exposure

Exposure will be summarized as dose received [cumulative dose, actual dose intensity (DI)] and as dose received relative to planned dose [relative dose intensity (RDI)]. Duration of

exposure to each study drug will be summarized as a continuous variable as well as in categories ($>0 \leq 4$, $>4 \leq 8$, $>8 \leq 12$, $>12 \leq 16$, $>16 \leq 20$, $>20 \leq 24$, and >24 weeks).

Exposure to AG-120 or matched placebo

The dose level for AG-120 or matched placebo is calculated as actual dose administered (mg/day). Only non-zero doses of AG-120 or matched placebo are considered in the derivations.

- Duration of exposure (days) = last dose date – first dose date + 1
- Cumulative dose (mg) = sum of the actual doses
- Planned DI (mg/day) = 500
- Actual DI (mg/day) = cumulative dose (mg) / duration of exposure (days)
- RDI (%) = $100 \times \text{Actual DI (mg/day)} / \text{Planned DI (mg/day)}$

Exposure to Azacitidine

The dose level for azacitidine is calculated as actual dose administered (mg/m²/day). In what follows, dose, last dose date and first dose date refer to azacitidine. Only non-zero doses are considered in the derivations.

- Planned duration of exposure (4-week cycle) = (start date of azacitidine last cycle – start date of azacitidine first cycle + 28) / 28
- Duration of exposure (4-week cycle) = (last dose date – first dose date + 1) / 28
- Cumulative dose (mg/m²) = sum of the actual doses
- Planned DI (mg/m²/4-week cycle) = 525
- Actual DI (mg/m²/4-week cycle) = cumulative dose (mg/m²) / [planned duration of exposure (4-week cycle)]
- RDI (%) = $100 \times \text{Actual DI (mg/m}^2\text{/4-week cycle)} / \text{Planned DI (mg/m}^2\text{/4-week cycle)}$

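### SAP 6.5.3 imputes an AG-120/placebo last-dose date outside the recorded month when that month lies in an earlier year than EOT or death

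*SAP*

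**What the plan says.** The scope is stated in SAP 6.5.3: "If the date of the last dose of study drug (AG-120 or matched placebo) is missing or partially missing, it will be imputed as follows". Where the subject has an EOT disposition page for the drug, or a death date by the cutoff, there are three outcomes:

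1. Year only recorded: "Last day of the year, if only the year is available and Year <Year of min (EOT date, death date").
2. Year and month recorded: the last day of that month, but only "if both the year and month are available and Year=Year of min(EOT date, death date") and the month is earlier.
3. Otherwise: "min(EOT date, death date), for all other cases".

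Azacitidine has its own rule in the same section and is not affected.

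The imputed date is used in two places:

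- **Exposure and dose intensity (SAP 7.4.1).** "Duration of exposure (days) = last dose date – first dose date + 1", and "Actual DI (mg/day) = cumulative dose (mg) / duration of exposure (days").
- **Safety window (SAP 6.3.5).** "The on-treatment period starts on the date of the start of study treatment and ends 28 days after the end of study treatment". SAP 6.3.2 takes the end of study treatment as the later of the two drugs' end dates.

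**The concern.** A recorded month is information about when dosing stopped, and an imputation should respect it. Line 2 does so within a calendar year but not across a year end, and line 1 is reserved for dates with no month. A subject whose last dose is known to be in a given month of the earlier year is therefore assigned a date in the following year or later.

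Neighbouring rules suggest an oversight rather than a deliberate conservative choice. SAP 6.5.5, for the start of new anticancer therapy, has a separate branch for a known month in an earlier year and returns "imputed start date=DAY (Last day of MMM) MMM YYYY". SAP 6.5.1 compares month and year jointly.

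At stake are AG-120/placebo duration of exposure and dose intensity. In some subjects the end of the on-treatment period is also affected, and that period decides which adverse events, laboratory values, transfusions and deaths count as on-treatment.

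**Working it through.** The plan states no figure on this point, so there is nothing to reproduce. The check is of the date logic as written. Let M be the earlier of the EOT and death dates.

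**Inputs.** The three lines of SAP 6.5.3; the exposure formulas of SAP 7.4.1; the 28-day window of SAP 6.3.5; the end-of-treatment definition of SAP 6.3.2. Protocol 10.1 puts the EOT visit within 1 week of the last dose, or no later than 4 weeks after it when a dose is held and treatment is then stopped. The calendar dates below are illustrative assumptions.

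**Step 1: which line applies.**

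| Recorded | M | Line used | Imputed date |
|---|---|---|---|
| Nov 2020 | 15 Dec 2020 | 2 | 30 Nov 2020 |
| 2020 only | 15 Jan 2021 | 1 | 31 Dec 2020 |
| Nov 2020 | 15 Jan 2021 | 3 | 15 Jan 2021 |
| Dec 2020 | 4 Jan 2021 | 3 | 4 Jan 2021 |

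The second and third rows show the anomaly: knowing the month as well as the year moves the imputed date further from the truth.

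**Step 2: how often, and by how much.** The rule was applied to each of 1,095 consecutive true last-dose days from 1 January 2018, with the day removed, for several gaps from last dose to M. Excess is measured from the last day of the recorded month, the latest date the record allows, so it is a lower bound on the true overstatement.

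| Gap to M | Days affected | Share | Excess (days) |
|---|---|---|---|
| 7 days (protocol) | 20 | 1.8% | 1–7 |
| 28 days (protocol, after a hold) | 83 | 7.6% | 1–28 |
| 60 days (assumed) | 179 | 16.3% | 30–60 |
| 180 days (assumed) | 539 | 49.2% | 150–180 |
| 365 days (assumed) | 1,094 | 99.9% | 335–365 |

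Every contradiction with the recorded month came from one situation: month known, year earlier than the year of M. The shares apply only among subjects whose stop date has a month and year but no day.

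**Step 3: exposure and dose intensity.** Take first dose 1 June 2020, last dose recorded as November 2020 and M = 15 January 2021.

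- As written: 1 June 2020 to 15 January 2021 = 229 days.
- Using the last day of the month: 1 June to 30 November 2020 = 183 days, so the excess is 229 − 183 = 46 days.
- With cumulative dose held at 500 × 183 = 91,500 mg, dose intensity is 91,500 / 229 = 399.6 mg/day (79.9% of 500) as written, against 91,500 / 183 = 500 mg/day (100%).

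In the December row of Step 1 the excess is only 4 days.

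**Step 4: on-treatment window.** In the November example, the window based on AG-120/placebo alone ends on 15 January + 28 days = 12 February 2021, instead of 30 November + 28 days = 28 December 2020. This shift carries through only if azacitidine ended by 30 November. A later azacitidine end date shrinks it, and one on or after 15 January removes it.

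**The case against.** The strongest reply is that the rule rarely operates and seldom matters.

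- **EOT timing.** With a gap of at most 4 weeks, a November last dose cannot have a January EOT, so only December stop dates are exposed. Protocol 9.11.1 also sets EOT at the date drug was first held when a toxicity hold is not followed by restart. This stands for the usual case, and the 46-day example lies outside that visit timing. It is not a complete answer. Protocol 10.1 times the EOT visit from the second drug stopped, so the gap can be longer if azacitidine continued and the EOT date is the visit date. SAP 6.5.3 refers to a disposition page for the drug in question, and the documents do not settle which date is meant.
- **Death without an EOT page.** The rule allows this, but Protocol 8.5 requires the reason for discontinuation to be recorded, so it would be a data-quality failure. It is possible but not expected.
- **Partial dates are uncommon.** Doses are documented in the eCRF (Protocol Table 6 footnotes). This stands.

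A reader might also infer more than the documents support:

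- **That the case has no rule.** It has one: the catch-all assigns a date, and that date is the problem.
- **That the on-treatment window is always lengthened.** SAP 6.3.2 uses the later of the two drugs, so it depends on the azacitidine end date.
- **That an EFS censoring date is moved directly.** SAP 6.5.5 does use the last dose of study treatment to impute a missing or partial start of new anticancer therapy. Under SAP Table 5, however, censoring is at the last adequate disease assessment, and the therapy start only helps select it. An effect would need an affected AG-120/placebo date later than the azacitidine end, a missing or partial therapy start, that imputed date to govern over the relapse and therapy-end dates, and an assessment falling between the two candidate dates. No such effect has been shown.

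**Conclusion.** The rule is wrong as written, and the consequence is minor. For a known month in an earlier year than the year of M, SAP 6.5.3 always returns a date outside the recorded month and year.

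AG-120/placebo exposure is always overstated in that situation. Dose intensity is understated provided cumulative dose is kept at the recorded doses; SAP 7.4.1 says only that actual doses are summed. The effect on the on-treatment window is conditional on azacitidine, and the effect on EFS is remote.

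Under protocol EOT timing the excess is 1 to 28 days, in a small fraction of an already small group. Larger errors rest on the assumption that EOT or death falls well after the last AG-120/placebo dose. The documents do not give the number of partial stop dates, so no count of affected subjects can be stated.

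**What to change.** Reword the second line of the AG-120/placebo rule in SAP 6.5.3 so that, when year and month are both recorded, the last day of the recorded month is used whenever that year-month is earlier than the year-month of the earlier of EOT and death. This covers an earlier year as well as an earlier month of the same year, and it matches SAP 6.5.5. In the check above it kept the imputed date in the recorded month for every day and gap tested.

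Leave the catch-all line exactly as it is. Restricting it to equal year-months or uninformative dates would leave a recorded year-month later than EOT or death without a rule.

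The cost is one SAP line and one line of derivation code. Make the change before unblinding, so that it cannot appear data-driven.

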6.5.4. Death Date

Missing or partial death dates will be imputed based on the last contact date (as derived in [Section 6.3.7](#)), as follows:

- If the death date is missing it will be imputed as the day after the date of last contact
- If the day is missing or both the day and month are missing, the death date will be imputed as follows:
 - Missing day only: max(1st day of the month and year of death, last contact date+1)
 - Missing day and month: max(01 January of the year of death, last contact date+1)

If the imputed death date is after the data cutoff date, the subject will be considered to be alive at the time of the data cutoff date.

6.5.5. Date of Start of New Anticancer Therapy

Incomplete dates for start of new anticancer therapy will be imputed and the imputed full date will be used for determining the censoring date for efficacy analyses as described in [Section 7](#). If the imputation results in an end date prior to the imputed start date, then the imputed start date will be set to the end date.

- The end date of new anticancer therapy will be included in the imputations for start date of new anticancer therapy. If the end date of new anticancer therapy is
 - Completely missing then it will be ignored in the imputations below
 - Partially missing with only year (YYYY) available then the imputations below will consider 31DECYYYY as the end date of the new anticancer therapy
 - Partially missing with only month and year available then the imputations below will consider the last day of the month for MMMYYYY as the end date of the new anticancer therapy
- For subjects who have not discontinued study treatment at the data cutoff date, last dose of study treatment is set to the data cutoff date in the imputations below.
- If the start date of new anticancer therapy is completely or partially missing, then the imputed start date of new anticancer therapy is derived as follows:
 - Start date of new anticancer therapy is completely missing
Imputed start date=min[max(relapse date+1, last dose of study treatment+1), end date of new anticancer therapy]
 - Only year (YYYY) for start of anticancer therapy is available

IF YYYY <Year of min[max(relapse date+1, last dose of study treatment+1), end date of new anticancer therapy]

THEN imputed start date=31DECYYYY

ELSE IF YYYY=year of min[max(relapse date+1, last dose of study treatment+1), end date of new anticancer therapy]

THEN imputed start date=min[max(relapse date+1, last dose of study treatment+1), end date of new anticancer therapy]

ELSE IF YYYY >Year of min[max(relapse date+1, last dose of study treatment+1), end date of new anticancer therapy]

THEN imputed start date=01JANYYYY

- Both year (YYYY) and month (MMM) for start of anticancer therapy are available

IF

YYYY=Year of min[max(relapse date+1, last dose of study treatment+1), end date of new anticancer therapy], AND

MMM <Month of min[max(relapse date+1 day, last dose of study treatment+1 day), end date of new anticancer therapy]

THEN

imputed start date=DAY (Last day of MMM) MMM YYYY ;

ELSE IF

YYYY=Year of min[max(relapse date+1, last dose of study treatment+1), end date of new anticancer therapy], AND

MMM=Month of min[max(relapse date+1 day, last dose of study treatment+1 day), end date of new anticancer therapy]

THEN

imputed start date=min[max(relapse date+1 day, last dose of study treatment+1 day), end date of new anticancer therapy];

ELSE IF

YYYY=Year of min[max(relapse date+1, last dose of study treatment+1), end date of new anticancer therapy], AND

MMM >Month of min[max(relapse date+1 day, last dose of study treatment+1 day), end date of new anticancer therapy]

THEN

imputed start date=01 MMM YYYY;

ELSE IF

```
        YYYY <Year of min[max(relapse date+1, last dose of study  
        treatment+1), end date of new anticancer therapy]  
    THEN  
        imputed start date=DAY (Last day of MMM) MMM YYYY  
    ELSE IF  
        YYYY >Year of min[max(relapse date+1, last dose of study  
        treatment+1), end date of new anticancer therapy]  
    THEN  
        imputed start date=01 MMM YYYY.
```

